9.2.3.12 Body Weight

Body weight measurements will be performed in accordance with “9.2.4.5 Height and Weight.”

9.2.3.13 Fasting Urine Glucose/Creatinine Ratio

Urine samples will be collected at the following visits for measurement at the central laboratory: the first day of the treatment period; and Weeks 4, 8, 12, 24, 36, 52, 64, 76, 88, and 104 of the treatment period (or at treatment period discontinuation, whenever possible). The urine samples will be collected by the central laboratory, and the test results printouts provided by the central laboratory will be retained by the study sites.

9.2.4 Safety Assessment Parameters

9.2.4.1 Clinical Laboratory Tests

Blood samples will be collected at the following visits for the measurement of the following parameters at the central laboratory: the first day of the run-in period; the first day of the treatment period; and Weeks 4, 8, 12, 16, 20, 24, 28, 32, 36, 40, 44, 48, 52, 64, 76, 88, and 104 of the treatment period (or at treatment period discontinuation).

(1) Hematology test parameters

White blood cell count, red blood cell count, hemoglobin, hematocrit, platelet count, white blood cell differential (neutrophils, lymphocytes, monocytes, eosinophils, basophils)

(2) Blood biochemistry test parameters (except for the parameters for the efficacy assessments)

AST (GOT), ALT (GPT), ALP, LDH, gamma-GTP, total cholesterol, LDL-C, CPK, Na, K, Cl, Ca, inorganic phosphorus, Mg, HCO₃, ketone body differential (total ketone bodies, acetoacetic acid, 3-hydroxybutyric acid), total protein, urea nitrogen, serum creatinine, uric acid, total bilirubin, direct bilirubin, albumin

Urine samples will be collected at the following time points for the measurement of the following parameters: the first day of the treatment period, and Weeks 4, 8, 12, 24, 36, 52, 64, 76, 88, and 104 of the treatment period (or at treatment period discontinuation).

(3) Urinalysis (quantitative) (except for the parameters for the efficacy assessments)

Urine creatinine, urine Na,* urine K,* urine Cl,* urine Ca,* urine inorganic phosphorus,* urine Mg*

*: Creatinine adjusted value

Urine samples will be collected at the following study visits for the measurement of the following parameters: the first day of the treatment period, and Weeks 4, 8, 12, 16, 20, 24, 28, 32, 36, 40, 44, 48, 52, 64, 76, 88, and 104 of the treatment period (or at treatment period discontinuation).

(4) Urinalysis (qualitative)

Specific gravity, pH, urine protein, urine occult blood, urine ketones, urine bilirubin, urine urobilinogen, nitrite, white blood cell esterase

The blood and urine samples will be collected by the individual study sites, and will then be collected from the study sites by the central laboratory for measurement. The test result printouts provided by the central laboratory will be retained by the study sites.

The clinical laboratory test results will be considered abnormal values if they deviate from the central laboratory's reference values.

If a urinary tract infection or genital infection is suspected, the necessary tests (e.g., bacteria tests) will be performed in order to arrive at a diagnosis.

9.2.4.2 Renal Function Biomarkers

Blood and urine samples will be collected at the study visits on the first day of the treatment period and at the visits at Weeks 52 and 104 of the treatment period (and at treatment period discontinuation whenever possible) for the measurement of the following parameters.

(1) Blood biochemistry parameters:

Serum cysteine C,^{*1} erythropoietin,^{*2} c-peptide, high sensitivity CRP

*1: The following formulas, which are formulas that use the serum cysteine C levels in Japanese, will be used to calculate the eGFRcys at the central laboratory.

Males: $eGFRcys \text{ (mL/min/1.73 m}^2\text{)} = (104 \times \text{serum cysteine C}^{-1.019} \times 0.996^{\text{Age}}) - 8$

Females: $eGFRcys \text{ (mL/min/1.73 m}^2\text{)} = (104 \times \text{serum cysteine C}^{-1.019} \times 0.996^{\text{Age}} \times 0.929) - 8$

Age: The subject's biological age in years

*2: Blood samples will also be collected for measurement at the visit at Week 4 of the treatment period.

(2) Urinalysis (quantitative):

Urine transferrin, NAG, L-FABP

(3) Other:

TNFR1, TNFR2

9.2.4.3 Pregnancy Tests (Women of Childbearing Potential Only)

A urine human chorionic gonadotropin (hCG) pregnancy test will be performed at the study visits on the first day of the run-in period and Weeks 24, 52, 76, and 104 of the treatment period (or at treatment period discontinuation), and the results will be entered in the case report form.

9.2.4.4 Vital Signs

Blood pressure and pulse rate will be measured, and the results entered into the case report form, at the study visits on the first day of the run-in period, the first day of the treatment period, Weeks 4, 8, 12, 16, 20, 24, 28, 32, 36, 40, 44, 48, 52, 64, 76, 88, and 104 of the treatment period (or at treatment period discontinuation). The measurements will be taken before blood sample collection, with the patient sitting down and having rested for at least 5 minutes. On the first day of the run-in period, blood pressure will be measured at both arms, and if the difference between the arms exceeds

10 mmHg for either the diastolic blood pressure or the systolic blood pressure, then the value from the arm with the higher reading will be used. If the difference between the arms is 10 mmHg or less, then the value from either arm may be used. As a rule, subsequent measurements will be taken using the same arm. In addition, whenever possible the same person should take the measurements each time to minimize inter-rater variability. Three blood pressure measurements will be taken at each visit, at intervals of at least 1 minute.

9.2.4.5 Height and Weight

Height will be measured on the first day of the treatment period at the study site, and the result entered in the case report form.

Weight will be measured at the study site on the first day of the run-in period, the first day of the treatment period, and at Weeks 12, 24, 36, 52, 64, 76, 88, and 104 of the treatment period, and the results entered into the case report form.

9.2.4.6 Resting Standard 12-Lead ECG

A resting standard 12-lead ECG will be measured at the subject visits on the first day of the run-in period, the first day of the treatment period, and Weeks 24, 52, 76, and 104 of the treatment period (or at treatment period discontinuation). The results of, for example, the arrhythmia and waveform diagnoses from the ECG results will be comprehensively assessed and classified according to the following 3 levels, and the result entered into the case report form.

- (1) Normal
- (2) Abnormal, NCS (Clinically insignificant abnormality)
- (3) Abnormal, CS (Clinically significant abnormality)

9.2.4.7 Hypoglycemia

The (sub) investigator will monitor the subject for hypoglycemia from the first day of the run-in period until Day 14 of the follow-up observation period based on Appendix 4, “Hypoglycemia Symptom Survey Form” and the blood glucose measurement results.

At each subject visit, the (sub) investigator will have the subject bring in the “Hypoglycemia Symptom Survey Form,” and will check its contents. If the (sub) investigator determines, on the basis of the “Hypoglycemia Symptom Survey Form” and the blood glucose measurement results, that the subject has developed hypoglycemia, the (sub) investigator will note this in the hypoglycemia space on the case report form. If the (sub) investigator determines that a symptom that is not judged to constitute hypoglycemia is an adverse event, the (sub) investigator will enter this information in the

adverse event section of the case report form.

The (sub) investigator will obtain the following information about events that have been judged to constitute hypoglycemia, and will record this information in the case report form in accordance with "9.2.4.8 Adverse Events." Furthermore, if the (sub) investigator determines that an event constitutes asymptomatic hypoglycemia, then the (sub) investigator will promptly check the subject's condition.

- (1) Hypoglycemia symptoms: Details of observed symptoms of hypoglycaemia.
 - (2) Hypoglycemia categories: Hypoglycemia will be classified based on the categories shown in Table 9.2 below.

Table 9.2: Hypoglycemia Categories

- (3) Severity
 - (4) Date and time of onset: The date and time when the hypoglycemia was noticed.
 - (5) Outcome, date of outcome, time of recovery
 - (6) Blood glucose level, date and time of blood glucose level measurement: The blood glucose level at the onset of hypoglycemia, and the date and time of the measurement.
 - (7) The cause of the hypoglycemia: The cause of the hypoglycemia will be determined based on the following criteria.
 - a) None
 - b) No diet or delay of diet
 - c) Performed intense exercise
 - d) Other
 - (8) Date and time of food eaten before the onset of hypoglycemia, date and time medicine was taken
 - (9) Action taken with respect to TA-7284
 - (10) Non-investigational product action(s) taken
 - (11) Causal relationship to TA-7284
 - (12) Seriousness

9.2.4.8 Adverse Events

An adverse event refers to any clinically untoward or unintended sign (including clinically

significant test abnormalities), symptoms, or disease observed after the first day of the treatment period, regardless of the causal relationship between the event and the investigational product. In addition, if a worsening of the event (e.g., a worsening of the severity of the event) occurs, it will be handled as a new adverse event. With the elimination half-life of TA-7284 in mind, the period for the collection of information about adverse events will be from the start of the treatment period investigational product administration through Day 14 of the follow-up observation period, during which time the (sub) investigator will determine what adverse events have occurred by, for example, questioning the subject.

Because placebos are the only investigational product that is going to be administered in the run-in period of this study, information about adverse events occurring during the run-in period will not be collected. However, an adverse event that occurs between the date of informed consent acquisition and the start of the treatment period investigational product administration that meets the criteria for classification as a “serious adverse event” will be reported to the study sponsor in accordance with “11.1 Actions Taken When a Serious Adverse Event Occurs.”

(1) Symptoms or diseases

The (sub) investigator will check for adverse events through interview or examination.

(2) Signs

The (sub) investigator will handle all clinically significant abnormalities* as adverse events.

* “Clinically significant abnormalities” are assessed according to the following criteria:

- The abnormality is related to a clinical sign or clinical symptom
The test abnormality need not be classified as an adverse event if the symptom or sign has already been reported as an adverse event.
- Medical or surgical treatment is administered in response to the test abnormality
- The administration of the investigational product is changed (e.g., dosage changed, drug withdrawn, discontinued) in response to the test abnormality
- The (sub) investigator otherwise determines that the abnormality is clinically significant

(3) Adverse event assessment and criteria

1) Day of onset

The day on which the symptom occurred or day of the test in which the laboratory abnormality was identified

2) Severity

The severity of adverse events will be classified according to the following criteria:

1. Mild: The event does not interfere with the daily activities of the subject.

2. Moderate: The event causes some interference with the daily activities of the subject.
3. Severe: The event makes the daily activities of the subject impossible.

3) Seriousness

The seriousness of adverse events will be classified as follows:

1. Not serious
2. Serious: (a) – (f)

- (a) Results in death
- (b) Is life-threatening
- (c) Requires inpatient hospitalisation or results in prolongation of existing hospitalisation
- (d) Results in persistent or significant disability/incapacity
- (e) Is a medically important event or reaction
- (f) Is a congenital anomaly / birth defect

4) Causal relationships to investigational product

The (sub) investigator will assess whether there is a reasonable possibility that the investigational product caused the adverse event. This assessment will be made in consideration of the underlying disease, concomitant medical diseases, and other aspects of the natural course of the primary disease, concomitant therapies, other risk factors and factors other than the investigational product, and the temporal relationship between investigational product dosing and adverse event onset (e.g., recurrence following rechallenge, resolution following discontinuation). Adverse events whose causal relationship with the investigational product is assessed as a reasonable possibility will be considered adverse drug reactions.

1. Reasonable possibility
2. No reasonable possibility

5) Outcome

The outcome of adverse events will be classified on the following 6-grade scale:

1. Resolved
2. Resolving
3. Not resolved
4. Resolved with sequelae
5. Fatal
6. Unknown

6) Day of outcome

The day of the outcome will be classified according to the criteria shown in Table 9.3 below.

Table 9.3: Outcome Day Criteria

Resolved	The day of resolution. However, if the day of resolution cannot be identified, then this will be the day on which the outcome was confirmed or determined.
Resolving	The day on which it was confirmed or determined that the subject was resolving.
Not resolved	The day on which it was confirmed or determined that the subject had not resolved.
Resolved with sequelae	The day on which it was confirmed or determined that sequelae were present.

- When a surgical procedure is not classified as an adverse event and the disease or symptoms necessitating the surgical procedure are known, these should be classified as adverse events.

10. Evaluation Methods and Criteria

10.1 Efficacy Endpoints

10.1.1 Primary Endpoint

The proportion of subjects with a 30% decline in the eGFR (the proportion of subjects with a decline of at least 30% in the eGFR at the end of the treatment period compared to the average of the values on the first days of the run-in and treatment periods).

10.1.2 Secondary Endpoints

- (1) The proportion of subjects with a 40% decline in the eGFR (the proportion of subjects with a decline of at least 40% in the eGFR at the end of the treatment period compared to the average of the values on the first days of the run-in and treatment periods)
- (2) The change and percent change in the eGFR at each assessment time point compared to the average of the values on the first days of the run-in and treatment periods
- (3) Composite endpoint of end-stage renal disease (ESRD), doubling of serum creatinine, renal death, and cardiovascular (CV) death
- (4) Composite endpoint of CV death and hospitalized congestive heart failure
- (5) Composite endpoint of CV death, non-fatal myocardial infarction, and non-fatal stroke
- (6) Hospitalized congestive heart failure
- (7) The renal composite endpoint of ESRD, doubling of serum creatinine, and renal death
- (8) CV death

- (9) All-cause death
- (10) The CV composite endpoint of CV death, non-fatal myocardial infarction, non-fatal stroke, hospitalized congestive heart failure, and hospitalized unstable angina
- (11) Percent change from the first day of the treatment period in urine ACR (first morning void urine) at each assessment time point
- (12) Change from the first day of the treatment period in the HbA1c at each assessment time point
- (13) Change from the first day of the treatment period in fasting blood glucose at each assessment time point
- (14) Change from the first day of the treatment period in blood pressure (systolic blood pressure, diastolic blood pressure) at each assessment time point
- (15) Change and percent change from the first day of the treatment period in the lipid levels (HDL-C, fasting neutral lipids) at each assessment time point
- (16) Change and percent change from the first day of the treatment period in body weight at each assessment time point
- (17) Change from the first day of the treatment period in the fasting urine glucose/creatinine ratio at each assessment time point

For the events described in (3) through (10), both the proportion of subjects with such events and the time to initial onset will be assessed.

10.2 Safety

Adverse events and adverse drug reactions (See Section “9.2.4.8, Adverse Events”)

11. Ensuring Subject Safety

11.1 Actions to Take for Serious Adverse Events

The (sub) investigator will immediately administer appropriate treatment to any subject suffering a serious adverse event between the informed consent acquisition and Week 4 of the follow-up observation period, regardless of the causal relationship with the investigational product.

In the event of a serious adverse event, the (sub) investigator will immediately notify a monitor (in writing, as a rule) and submit detailed information in writing within 7 days of notifying the monitor. The investigator will inform the director of the study site about any such serious adverse event.

Definition of serious adverse events

- (1) Results in death
- (2) Is life-threatening
- (3) Requires inpatient hospitalisation or results in prolongation of existing hospitalisation
- (4) Results in persistent or significant disability/incapacity
- (5) Is a medically important event or reaction
- (6) Is a congenital anomaly / birth defect

11.2 Significant Adverse Events

There are no clinically significant adverse events that need to be defined for the purpose of investigating the safety profile.

11.3 Noteworthy Issues

The (sub) investigator will conduct the study paying close attention to safety, in accordance with the [REDACTED] from Appendix 2 issued by the Committee on the Appropriate Use of SGLT2 Inhibitors.

Prior to the day of informed consent acquisition, the (sub) investigator will provide subjects with guidance on getting enough fluids during the study, and will monitor the subjects closely for any decrease in total body fluid associated with polyuria/pollakiuria, and if any abnormalities, such as dehydration or decreased blood pressure are found, the (sub) investigator will initiate appropriate measures, such as fluid supplementation, and determine whether or not the study should be discontinued, depending on the patient's condition.

If a subject develops fever, diarrhea, or vomiting, or cannot consume enough food because of anorexia (sick days), TA-7284 use should be temporarily discontinued.

11.4 Pregnancy Reporting, and Other Information Affecting Safety That Needs to be Reported to the Study Sponsor

On learning that an embryo or fetus of a female subject or the female partner of a male subject has been exposed to the investigational product prior to the completion of the required period for contraception (until Week 4 of the follow-up observation period), the (sub) investigator will immediately submit the [REDACTED] included in Appendix 1 to the sponsor. If the female subject (or the female partner of a male subject) wishes for the pregnancy to proceed to term, the (sub) investigator will follow the subject until delivery whenever possible, determine whether the neonate has been affected by the investigational product, enter the information determined in the [REDACTED] in Appendix 1, and submit the report to the sponsor.

If a subject experiences an event during the safety assessment period that the study sponsor has determined needs to be reported to the sponsor, even if the event does not constitute a serious adverse event, if the study sponsor so requires, detailed information about the event should be reported promptly to the study sponsor in writing regardless of the presence or absence of a causal relationship to the investigational product.

11.5 Notifying Other Doctors of Subjects

The (sub) investigator will determine at all subject visits whether each subject has received care at a setting unrelated to this clinical study. The (sub) investigator with the permission of the subject will notify the doctor of any subject receiving care by another doctor of the subject's participation in the study. The (sub) investigator or a clinical research coordinator will provide a study participation card to subjects for notifying other doctors via the subject of subject participation in the study and instruct the subjects to present the card on receiving care at another hospital or in another department.

12. Subject Discontinuation Criteria and Procedures

12.1 Discontinuation Criteria

Subjects meeting any of the following discontinuation criteria will be discontinued from the study.

- (1) If the subject requests discontinuation.
- (2) If it is determined that the subject is clearly ineligible to participate in the study.
- (3) If the (sub) investigator determines that it would be difficult to continue the study because of the emergence of, for example, an adverse event.
- (4) If the (sub) investigator determines that it would not be appropriate to continue the study because of a worsening of the patient's primary disease.
- (5) If it is discovered that the subject is pregnant.
- (6) If the (sub) investigator determines that the study should be discontinued for some other reason.

Rationale

(1)-(6) These criteria were established to allow the study to be ethically conducted and in consideration of subject safety.

12.2 Discontinuation Procedures

The (sub) investigator will take the appropriate actions for any subject who is discontinued from the study and promptly notify a monitor that the subject has been discontinued. The (sub) investigator will perform the tests and observations scheduled for discontinuation within 7 days of the treatment period discontinuation.

The follow-up observation period begins once the treatment period has been discontinued.

The (sub) investigator will record the date of discontinuation and the reason for discontinuation in the case report form. Furthermore, if the study is discontinued because of an adverse event, the term of the event that resulted in discontinuation will be recorded in the case report form. The date of discontinuation is the day on which evaluations on discontinuation (evaluation day) are performed or, when evaluations on discontinuation are not possible, the day on which the decision to discontinue the

subject was made.

For subjects for whom the observations/tests that should have been conducted at discontinuation could not be conducted, and for subjects who did not visit the study site following discontinuation, the reason(s) therefor, and the courses of the subjects following discontinuation, will be determined through follow-up investigations performed through written correspondence or telephone calls, and the information obtained will be recorded.

The (sub) investigator or a clinical research coordinator will whenever possible collect the Hypoglycemia Symptom Survey Forms of subjects who do not visit to the study site by, for example, having the subjects mail them back.

13. Statistical Analysis

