9.2.3.6 Other Events

Subjects will be monitored for the emergence of other events from the first day of the treatment period until Week 4 of the follow-up observation period.

The (sub) investigator will evaluate all individually diagnosed cases of hospitalized congestive heart failure, hospitalized unstable angina, all-cause death, non-fatal myocardial infarction, and non-fatal stroke, and will record the details in the case report form.

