4.10. Periods of Assessment of Efficacy Endpoint Events

4.10.1. Time to Initial Event Onset (in days)

Time to initial event onset = Day of initial event onset – First day of the treatment period + 1

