4.10.2. Time to Censoring (in days)

1. Subjects for whom the date of the visit at Week 4 of the follow-up observation period can be obtained

Time to censoring = Date of the visit at Week 4 of the follow-up observation period – First day of the treatment period + 1

2. Subjects for whom the date of the visit at Week 4 of the follow-up observation period can not be obtained

Time to censoring = Final assessment time point^{*1} – First day of the treatment period + 1

^{*1}Final assessment time point

If the day of discontinuation can be obtained: Day of discontinuation

If the day of discontinuation cannot be obtained: Day of the final scheduled visit^{*2}

^{*2}Day of the final scheduled visit

The latest date will be used, regardless of the allowable time window

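### Without a Week 4 follow-up visit, event time and person-time run to the discontinuation date, which can be an administrative decision day, with no stop at death or last known status (minor)

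*Protocol*

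**What the plan says.** SAP 4.10.2 sets the censoring time for the efficacy events, and SAP 4.13 sets the assessment period for the safety rates per 1000 person-years. Both use the date of the Week 4 follow-up visit when there is one. When there is not, both say "If the day of discontinuation can be obtained: Day of discontinuation". The fallback is "If the day of discontinuation cannot be obtained: Day of the final scheduled visit", so the last visit matters only if no discontinuation date exists.

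Protocol 12.2 makes that date the evaluation day, with one exception: "when evaluations on discontinuation are not possible, the day on which the decision to discontinue the" (the sentence ends by naming the subject). In that case an administrative decision day takes its place. Section 12.2 also requires the later course of subjects who could not be evaluated, or who stopped attending, to be obtained. This "will be determined through follow-up investigations performed through written correspondence or telephone calls", and what is learned is recorded.

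Protocol 9.2.3.6 monitors events "from the first day of the treatment period until Week 4 of the follow-up observation period", and sections 9.2.3.2, 9.2.3.4 and 9.2.3.5 set the same window for ESRD, renal death and CV death. SAP 4.10.1 defines event time as "Time to initial event onset = Day of initial event onset – First day of the treatment period + 1". SAP 6.4 says only that these event and censoring times are used for the 14 event categories.

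**The concern.** A censoring date should be the last day on which the subject was alive and event status was known. The decision day need not be that. If it falls after last contact, the days between were not observed but count as event-free. If it falls after death, the subject stays in risk sets for events that can no longer occur.

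The second problem runs the other way. Monitoring continues to Week 4 of follow-up and event time is not capped at the subject's censoring day. An event reported by telephone after discontinuation can then be counted on its onset day, while a subject reported event-free in a similar call is censored back at discontinuation. Follow-up length would then depend on outcome.

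The outputs at stake are those of SAP 7.6.2.4 (Kaplan-Meier curves, stratified Cox hazard ratios, event rates) and the safety rates of SAP 7.7.1. A difference between arms could arise if loss to follow-up differs by arm.

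**Working it through.** The plan states no figure to reproduce. The check traces the rule and then sizes it.

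**Which subjects are exposed**

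| Situation, no Week 4 follow-up visit | Time at risk ends | Consequence |
|---|---|---|
| Discontinuation evaluation done | Evaluation day | Later telephone-confirmed event-free time is dropped |
| Evaluation not possible, subject lost | Decision day | Days from last contact to decision count as event-free, unless status is later learned |
| Evaluation not possible, subject died | Decision day | Days from death to decision count where the death is not the event, if the decision is dated later |
| No discontinuation date | Last scheduled visit | No days counted beyond that visit |

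**Where a death is not the endpoint event** (14 categories in SAP 7.6.2.4)

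- CV death is the event in 6 (categories 1, 2, 3, 6, 7, 8) and is left to the censoring rule in 14 − 6 = 8.
- Renal death is the event in 4 (categories 1, 5, 7, 11) and is left to the rule in 14 − 4 = 10.
- Any other death is the event only in category 7 and is left to the rule in 14 − 1 = 13.
- The safety person-time of SAP 4.13 has no stop at death. The day of death is recorded (Protocol Table 9.3) but not used for censoring.

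**Size**

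Inputs from the documents: 150 subjects per arm; Week 104 at day 728; follow-up visit 28-42 days later; laboratory visits at Weeks 52, 64, 76, 88 and 104, so 12-16 weeks (84-112 days) apart in the second year. Protocol Table 9.1 nevertheless sets time points every 4 weeks throughout, and the schedule has a telephone follow-up row.

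Assumptions, not in the documents: 5-10 affected subjects per arm; a lag of 28 days (one contact interval) up to 112 days (the longest laboratory interval).

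Full follow-up per arm: 150 × (728 + 28 + 1) / 365.25 = 310.9 person-years.

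Spurious time = subjects × lag / 365.25:

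- 5 × 28 / 365.25 = 0.38 person-years (0.12%)
- 10 × 28 / 365.25 = 0.77 person-years (0.25%)
- 10 × 112 / 365.25 = 3.07 person-years (0.99%)

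Dropped telephone time, if 5-10 subjects per arm had status confirmed over the 28-42 day follow-up:

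- 5 × 28 / 365.25 = 0.38 person-years (0.12%)
- 10 × 42 / 365.25 = 1.15 person-years (0.37%)

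The two effects on person-time have opposite signs and partly offset each other.

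**The case against.** The strongest reply is that few subjects are involved and little time. The rule applies only without a Week 4 follow-up visit. The decision day applies only when no evaluation was possible, although one is due within 7 days of discontinuation. With contact scheduled about every 4 weeks, loss should normally show at about 28 days. A Cox estimate changes only if another subject in the same stratum has an event during the extra days. All of this stands, and it is why the point is minor.

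A reader might infer that subjects who die are routinely kept at risk after death. The documents do not support that. They do not say that a site dates its decision later than the death; it may use the day of death. Protocol 11.1 requires immediate notification of a death as a serious adverse event. A death of unknown cause is classed as CV death, which is itself the event in six categories. What remains is that nothing in 12.2 or the SAP rules post-death time out.

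A reader might also infer that events reported after discontinuation are certain to be counted. That is plausible from the monitoring window and the event-time formula, but SAP 6.4 has no rule for an event dated after the censoring day. The supported statement is that the handling is undefined and can be asymmetric.

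SAP section 6 leaves some data-handling issues to the sponsor's case review board. Case-by-case decisions do not replace a prespecified censoring rule.

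**Conclusion.** The point holds as a minor defect in the censoring and person-time rule. The SAP can count unobserved days, and under a stated condition days after death, as event-free, and it leaves undefined the treatment of events learned after discontinuation. Under the assumptions above, spurious time is 0.1-0.25% of person-time per arm with a 28-day lag. It reaches about 1% with a 112-day lag, which is plausible mainly for doubling of creatinine and sustained eGFR below 15, since both need central-laboratory measurements. The number of affected subjects and the lag are assumed; the documents give neither.

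It would go too far to conclude that the hazard ratios are materially biased. No difference between arms in loss to follow-up is documented. The primary eGFR endpoint does not use these times and is unaffected. The possible asymmetry between counted events and dropped event-free time matters more for its direction than for its amount.

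**What to change.** Change the SAP only.

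- **SAP 4.10.2**, subjects without a Week 4 follow-up visit: end time at risk at the earliest of death, the last date on which event status was known (visit, telephone or letter), and the end of the Week 4 follow-up window. For sustained eGFR below 15 and doubling of creatinine, take the last central-laboratory measurement as the last known status, because a call cannot establish it. Apply the same cut-off to events.
- **SAP 4.13**: end person-time at the earlier of death and last known status, and do not extend it beyond the collection window of the event being counted. For non-serious adverse events that window closes on Day 14 of follow-up (Protocol 9.2.4.8); running on to a later telephone contact would dilute their rates.
- **Protocol 12.2**: leave the discontinuation date as it is. SAP 4.6.2 and 4.7.2 use it for exposure duration and compliance, which a new definition would alter.

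The day of death and the information from post-discontinuation contacts are already to be recorded. The cost is a little extra derivation work and endpoint-specific censoring dates. ESRD and the composites containing it mix laboratory and non-laboratory components, so the SAP must state which date governs them.
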